7.2.9.2 Diaries

Subjects or subjects' parent or legally-authorized representative will be required to complete the following:

- Intake diaries, completed daily, which will include:
 - PN/IV volume and calories (days per week, hours per day)
 - EN (formula and specialized electrolyte solutions) volume and calories (days per week, hours per day)
 - Other nutrition (regular diet and drink) intake (to be converted into calories by site personnel)
- Urine/stool output diary, completed every day during the screening period and for 2 days (48 hours) just prior to every scheduled visit and telephone contact, consisting of:
 - Collection of urine data:
 - For those who are toilet trained and NOT IN DIAPERS: All urine output should be measured and recorded in mL. The subject or parent/legally-authorized representative will perform dipstick specific gravity tests on the first urine produced after the daily infusions of PN/IV support.
 - For those who are not toilet trained and IN DIAPERS: The weight of all urine-only diapers will be recorded. Volume will be calculated based on the formula: 1g (scale weight)=1 mL or 1 cc. At the discretion of the investigator, the parent/legally-authorized representative may be asked to collect the first void after the daily infusion of PN/IV support to measure the specific gravity.
 - Collection of stool output data (including stool only and mixed urine/stool diapers):
 - For those who are toilet trained and NOT IN DIAPERS: Daily stool count will be recorded.
 - For those who are not toilet trained and IN DIAPERS: The weight of all diapers that contain stool (including diapers that contain mixed stool and urine) will be recorded as stool output. Stool volume will be calculated based on the formula: 1 g (scale weight=1 mL or 1 cc).

- All ostomy output will be recorded as stool output and measured in cc or mL.
- In addition all subjects (toilet trained or not) will record the consistency (form) of the stool passed each day during the 48-hour period prior to each visit. The subjects/parent or legally-authorized representative of subject will use the Bristol Stool Form Scale (Lewis and Heaton, 1997) to make the assessment.

All diaries will be reviewed by the investigator or their designee at each visit or telephone contact to assess clinical status and opportunity for PN/IV changes and advance in feeds. At each visit, the diaries will be reviewed for completeness and accuracy of the data.

8 ADVERSE AND SERIOUS ADVERSE EVENT ASSESSMENTS

8.1 Definitions of Adverse Events, Period of Observation, Recording of Adverse Events

An AE is any untoward medical occurrence in a clinical investigation subject administered a pharmaceutical product and that does not necessarily have a causal relationship with this treatment. An AE can therefore be any unfavorable and unintended sign (including an abnormal laboratory finding), symptom, or disease temporally associated with the use of a medicinal (investigational) product, whether or not related to the medicinal (investigational) product (International Conference on Harmonisation [ICH] Guidance E2A 1995).

All AEs are collected from the time the informed consent/assent is signed until the defined follow-up period stated in Section 7.1.3. This includes events occurring during the screening phase of the study, regardless of whether or not investigational product is administered. Where possible, a diagnosis rather than a list of symptoms should be recorded. If a diagnosis has not been made, then each symptom should be listed individually. All AEs should be captured on the appropriate AE pages in the eCRF and in source documents. In addition to untoward AEs, unexpected benefits outside the investigational product indication should also be captured on the AE eCRF.

All AEs must be followed to closure (the subject's health has returned to his/her baseline status or all variables have returned to normal), regardless of whether the subject is still participating in the study. Closure indicates that an outcome is reached, stabilization achieved (the investigator does not expect any further improvement or worsening of the event), or the event is otherwise explained. When appropriate, medical tests and examinations are performed so that resolution of event(s) can be documented.

8.1.1 Severity Categorization

The severity of AEs must be recorded during the course of the event including the start and stop dates for each change in severity. An event that changes in severity should be captured as a new event. Worsening of pre-treatment events, after initiation of investigational product, must be recorded as new AEs (for example, if a subject experiences mild intermittent dyspepsia prior to dosing of investigational product, but the dyspepsia becomes severe and more frequent after first dose of investigational product has been administered, a new AE of severe dyspepsia [with the appropriate date of onset] is recorded on the appropriate eCRF).

The medical assessment of severity is determined by using the following definitions:

Mild:

A type of AE that is usually transient and may require only minimal treatment or therapeutic intervention. The event does not generally interfere with usual activities of daily living.

Moderate: A type of AE that is usually alleviated with specific therapeutic intervention. The event interferes with usual activities of daily living, causing discomfort but poses no significant or permanent risk of harm to the research subject.

Severe: A type of AE that interrupts usual activities of daily living, or significantly affects clinical status, or may require intensive therapeutic intervention.

8.1.2 Relationship Categorization

A physician/investigator must make the assessment of relationship to investigational product for each AE. The investigator should decide whether, in his or her medical judgment, there is a reasonable possibility that the event may have been caused by the investigational product. If there is no valid reason for suggesting a relationship, then the AE should be classified as "not related". Otherwise, if there is any valid reason, even if undetermined or untested, for suspecting a possible cause-and-effect relationship between the investigational product and the occurrence of the AE, then the AE should be considered "related." The causality assessment must be documented in the source document.

The following additional guidance may be helpful:

Term	Relationship Definition
Related	The temporal relationship between the event and the administration of the investigational product is compelling and/or follows a known or suspected response pattern to that product, and the event cannot be explained by the subject's medical condition, other therapies, or accident.
Not Related	The event can be readily explained by other factors such as the subject's underlying medical condition, concomitant therapy, or accident and no plausible temporal or biologic relationship exists between the investigational product and the event.

8.1.3 Outcome Categorization

The outcome of AEs must be recorded during the course of the study on the eCRF. Outcomes are as follows:

- Fatal
- Not Recovered/Not Resolved
- Recovered/Resolved
- Recovered/Resolved With Sequelae
- Recovering/Resolving
- Unknown

8.1.4 Symptoms of the Disease Under Study

Symptoms of the disease under study should not be classed as AEs as long as they are within the normal day-to-day fluctuation or expected progression of the disease and are part of the efficacy

data to be collected in the study; however, significant worsening of the symptoms should be recorded as an AE.

8.1.5 Clinical Laboratory and Other Safety Evaluations

A change in the value of a clinical laboratory, vital sign, or ECG assessment can represent an AE if the change is clinically relevant or if, during treatment with the investigational product, a shift of a parameter is observed from a normal value to an abnormal value, or a further worsening of an already abnormal value. When evaluating such changes, the extent of deviation from the reference range, the duration until return to the reference range, either while continuing treatment or after the end of treatment with the investigational product, and the range of variation of the respective parameter within its reference range, must be taken into consideration.

If, at the end of the treatment phase, there are abnormal clinical laboratory, vital sign, or ECG values which were not present at the pre-treatment value observed closest to the start of study treatment, further investigations should be performed until the values return to within the reference range or until a plausible explanation (eg, concomitant disease) is found for the abnormal values.

The investigator should decide, based on the above criteria and the clinical condition of a subject, whether a change in a clinical laboratory, vital sign, or ECG parameter is clinically significant and therefore represents an AE.

8.1.6 Pregnancy

All pregnancies are to be reported from the time informed consent/assent is signed until the defined follow-up period stated in Section 7.1.3.

Any report of pregnancy for any female study participant must be reported within 24 hours to the Shire Global Pharmacovigilance and Risk Management Department using the Shire Investigational and Marketed Products Pregnancy Report Form. A copy of the Shire Investigational and Marketed Products Pregnancy Report Form (and any applicable follow-up reports) must also be sent to the Shire Medical Monitor using the details specified in the emergency contact information section of the protocol. The pregnant female study participant must be withdrawn from the study.

Every effort should be made to gather information regarding the pregnancy outcome and condition of the infant. It is the responsibility of the investigator to obtain this information within 30 calendar days after the initial notification and approximately 30 calendar days postpartum.

Pregnancy complications such as spontaneous abortion/miscarriage or congenital abnormality are considered SAEs and must be reported using the Shire Clinical Study Serious Adverse Event and Non-serious AEs Required by the Protocol Form. Note: An elective abortion is not considered an SAE.

In addition to the above, if the investigator determines that the pregnancy meets serious criteria, it must be reported as an SAE using the Shire Clinical Study Serious Adverse Event and Nonserious AEs Required by the Protocol Form as well as the Shire Investigational and Marketed Products Pregnancy Report Form. The test date of the first positive serum/urine β -HCG test or ultrasound result will determine the pregnancy onset date.

8.1.7 Abuse, Misuse, Overdose, and Medication Error

Abuse, misuse, overdose, or medication error (as defined below) must be reported to the sponsor according to the SAE reporting procedure whether or not they result in an AE/SAE as described in Section 8.2. Note: The 24-hour reporting requirement for SAEs does not apply to reports of abuse, misuse, overdose, or medication errors unless these result in an SAE.

The categories below are not mutually exclusive; the event can meet more than 1 category.

- Abuse Persistent or sporadic intentional intake of investigational product when used for a non-medical purpose (eg, to alter one's state of consciousness or get high) in a manner that may be detrimental to the individual and/or society
- **Misuse** Intentional use of investigational product other than as directed or indicated at any dose (Note: this includes a situation where the investigational product is not used as directed at the dose prescribed by the protocol.)
- **Overdose** Intentional or unintentional intake of a dose of an investigational product exceeding a pre-specified total daily dose of 0.05 mg/kg/day of the product.
- **Medication Error** An error made in prescribing, dispensing, administration, and/or use of an investigational product. For studies, medication errors are reportable to the sponsor only as defined below.

Cases of subjects missing doses of the investigational product are not considered reportable as medication errors.

Medication errors should be collected/reported for all products under investigation.

The administration and/or use of an expired investigational product should be considered as a reportable medication error.

All investigational product provided to pediatric subjects should be supervised by the parent/legally-authorized representative/caregiver.

8.2 Serious Adverse Event Procedures

8.2.1 **Reference Safety Information**

The reference for safety information for this study is the Investigator's Brochure which the sponsor has provided under separate cover to all investigators.

8.2.2 **Reporting Procedures**

All initial and follow-up SAE reports must be reported by the investigator to the Shire Global Pharmacovigilance and Risk Management Department and the Shire Medical Monitor or designee within 24 hours of the first awareness of the event. Note: The 24-hour reporting

Shire	CONFIDENTIAL	18 Dec 2015
Protocol SHP633-302	Version 1.0, Final	Page 51 of 70

requirement for SAEs does not apply to reports of abuse, misuse, overdose, or medication errors (refer to Section 8.1.7) unless they result in an SAE.

The investigator must complete, sign, and date the Shire Clinical Study Serious Adverse Event and Non-serious AEs Required by the Protocol Form and verify the accuracy of the information recorded on the form with the corresponding source documents (Note: Source documents are not to be sent unless requested) and fax or e-mail the form to the Shire Global Pharmacovigilance and Risk Management Department. A copy of the Shire Clinical Study Serious Adverse Event and Non-serious AEs Required by the Protocol Form (and any applicable follow-up reports) must also be sent to the Shire Medical Monitor or designee using the details specified in the emergency contact information section of the protocol.

8.2.3 Serious Adverse Event Definition

A serious adverse event (SAE) is any untoward medical occurrence (whether considered to be related to investigational product or not) that at any dose:

- Results in death
- Is life-threatening. Note: The term "life-threatening" in the definition of "serious" refers to an event in which the subject was at risk of death at the time of the event; it does not refer to an event which hypothetically might have caused death if it was more severe.
- Requires inpatient hospitalization or prolongation of existing hospitalization. Note: Hospitalizations, which are the result of elective or previously scheduled surgery for pre-existing conditions, which have not worsened after initiation of treatment, should not be classified as SAEs. For example, an admission for a previously scheduled ventral hernia repair would not be classified as an SAE; however, complication(s) resulting from a hospitalization for an elective or previously scheduled surgery that meet(s) serious criteria must be reported as SAE(s).
- Results in persistent or significant disability/incapacity
- Is a congenital abnormality/birth defect
- Is an important medical event. Note: Important medical events that may not result in death, be life-threatening, or require hospitalization may be considered an SAE when, based upon appropriate medical judgment, they may jeopardize the subject and may require medical or surgical intervention to prevent 1 of the outcomes listed in this definition. Examples of such medical events include allergic bronchospasm requiring intensive treatment in an emergency room or at home; blood dyscrasias or convulsions that do not result in inpatient hospitalization; or the development of drug dependency or drug abuse.

8.2.4 Serious Adverse Event Collection Time Frame

All SAEs (regardless of relationship to study) are collected from the time the informed consent/assent is signed until the defined follow-up period stated in Section 3.2 and must be reported to the Shire Global Pharmacovigilance and Risk Management Department and the Shire Medical Monitor or designee within 24 hours of the first awareness of the event.

Shire	CONFIDENTIAL	18 Dec 2015
Protocol SHP633-302	Version 1.0, Final	Page 52 of 70

In addition, any SAE(s) considered "related" to the investigational product and discovered by the investigator at any interval after the study has completed must be reported to the Shire Global Pharmacovigilance and Risk Management Department within 24 hours of the first awareness of the event.

8.2.5 Serious Adverse Event Onset and Resolution Dates

The onset date of the SAE is defined as the date the event meets serious criteria. The resolution date is the date the event no longer meets serious criteria, the date the symptoms resolve, or the event is considered chronic. In the case of hospitalizations, the hospital admission and discharge dates are considered the onset and resolution dates, respectively.

In addition, any signs or symptoms experienced by the subject after signing the informed consent/assent form, or leading up to the onset date of the SAE, or following the resolution date of the SAE, must be recorded as an AE, if appropriate.

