8.2.3 Serious Adverse Event Definition

An SAE is any untoward medical occurrence (whether considered to be related to investigational product or not) that at any dose:

- Results in death
- Is life-threatening. Note: The term "life-threatening" in the definition of "serious" refers to an event in which the subject was at risk of death at the time of the event; it does not refer to an event which hypothetically might have caused death if it was more severe.
- Requires inpatient hospitalization or prolongation of existing hospitalization. Note: Hospitalizations, which are the result of elective or previously scheduled surgery for pre-existing conditions, which have not worsened after initiation of treatment, should not be classified as SAEs. For example, an admission for a previously scheduled ventral hernia repair would not be classified as an SAE; however, complication(s) resulting from a hospitalization for an elective or previously scheduled surgery that meet(s) serious criteria must be reported as SAE(s).
- Results in persistent or significant disability/incapacity
- Is a congenital abnormality/birth defect
- Is an important medical event. Note: Important medical events that may not result in death, be life-threatening, or require hospitalization may be considered an SAE when, based upon appropriate medical judgment, they may jeopardize the subject and may require medical or surgical intervention to prevent 1 of the outcomes listed in this definition. Examples of such medical events include allergic bronchospasm requiring intensive treatment in an emergency room or at home; blood dyscrasias or convulsions that do not result in inpatient hospitalization; or the development of drug dependency or drug abuse.

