8.2.5 Serious Adverse Event Onset and Resolution Dates

The onset date of the SAE is defined as the date the event meets serious criteria. The resolution date is the date the event no longer meets serious criteria, the date the symptoms resolve, or the event is considered chronic. In the case of hospitalizations, the hospital admission and discharge dates are considered the onset and resolution dates, respectively.

In addition, any signs or symptoms experienced by the subject after signing the informed consent/assent form, or leading up to the onset date of the SAE, or following the resolution date of the SAE, must be recorded as an AE, if appropriate.

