9.9 Safety Analyses

The safety and tolerability variables include:

- Adverse events, including those pertaining to GI symptoms
- Body weight, height (or length), head circumference (up to 36 months of age), and trends on growth charts
- Vital signs, including temperature, heart rate, blood pressure
- Electrocardiograms
- Laboratory safety data (ie, biochemistry, hematology, coagulation, urinalysis) including the following lab tests at all site visits and interim safety labs to detect hepatoxicity signals: AST, ALT, ALP, and bilirubin
- Urine output (measured volume)
- Fecal output (by volume or number of bowel movements per day)
- Antibodies to teduglutide
- GI-specific testing including colonoscopy or sigmoidoscopy, abdominal ultrasound, fecal occult blood testing, UGI/SBFT

Adverse events will be coded using MedDRA. Treatment-emergent AEs will be summarized by system organ class and preferred term. The number and percentage of subjects with AEs, SAEs, AEs that lead to discontinuation, investigational product-related AEs (determined by the investigator), and AEs that resulted in a fatal outcome will be summarized. AEs will also be summarized with regard to intensity and relationship to investigational product. For AEs of special interest, the CTCAE grading system will be used as described in Section 8.4.1.

For laboratory tests, vital signs, body weight, ECG, and output diary variables, descriptive statistics (mean, median, standard deviation, minimum and maximum values, the number and percentage of subjects in specified categories) will be calculated to summarize the absolute values and change from baseline at each scheduled visit.

The number and percentage of subjects classified as having positive specific antibodies to teduglutide will be used to summarize the presence of antibodies.

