8 ADVERSE AND SERIOUS ADVERSE EVENT ASSESSMENTS

8.1 Definitions of Adverse Events, Period of Observation, Recording of Adverse Events

An AE is any untoward medical occurrence in a clinical investigation subject administered a pharmaceutical product and that does not necessarily have a causal relationship with this treatment. An AE can therefore be any unfavorable and unintended sign (including an abnormal laboratory finding), symptom, or disease temporally associated with the use of a medicinal (investigational) product, whether or not related to the medicinal (investigational) product (International Conference on Harmonisation [ICH] Guidance E2A 1995).

All AEs are collected from the time the informed consent/assent is signed until the defined follow-up period stated in Section 3.2. This includes events occurring during the screening phase of the study, regardless of whether or not investigational product is administered. Where possible, a diagnosis rather than a list of symptoms should be recorded. If a diagnosis has not been made, then each symptom should be listed individually. All AEs should be captured on the appropriate AE pages in the eCRF and in source documents. In addition to untoward AEs, unexpected benefits outside the investigational product indication should also be captured on the AE eCRF.

All AEs must be followed to closure (the subject's health has returned to his/her baseline status or all variables have returned to normal), regardless of whether the subject is still participating in the study. Closure indicates that an outcome is reached, stabilization achieved (the investigator does not expect any further improvement or worsening of the event), or the event is otherwise explained. When appropriate, medical tests and examinations are performed so that resolution of event(s) can be documented.

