8.1.1 Severity Categorization

The severity of AEs must be recorded during the course of the event including the start and stop dates for each change in severity. An event that changes in severity should be captured as a new event. Worsening of pre-treatment events, after initiation of investigational product, must be recorded as new AEs (for example, if a subject experiences mild intermittent dyspepsia prior to dosing of investigational product, but the dyspepsia becomes severe and more frequent after first dose of investigational product has been administered, a new AE of severe dyspepsia [with the appropriate date of onset] is recorded on the appropriate eCRF).

The medical assessment of severity is determined by using the following definitions:

Mild:

A type of AE that is usually transient and may require only minimal treatment or therapeutic intervention. The event does not generally interfere with usual activities of daily living.

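### The admission-date rule for SAE onset (Protocol, Section 8.2.5) has no exception for events that arise during a hospital stay, so an SAE that prolongs a stay is dated before it happened

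*Protocol*

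**What the plan says.** Section 8.2.5 gives a general onset rule: "The onset date of the SAE is defined as the date the event meets serious criteria". Its second sentence gives a general resolution rule: "The resolution date is the date the event no longer meets serious criteria, the date the symptoms resolve, or the event is considered chronic". The third sentence is specific to hospital stays: "In the case of hospitalizations, the hospital admission and discharge dates are considered the onset and resolution dates, respectively".

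The next paragraph of 8.2.5 deals with what falls outside those dates. Signs or symptoms "leading up to the onset date of the SAE, or following the resolution date of the SAE, must be recorded as an AE, if appropriate".

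The hospitalization criterion in Section 8.2.3 has two limbs: "Requires inpatient hospitalization or prolongation of existing hospitalization". The note to that criterion says that admission for elective or previously scheduled surgery is not an SAE if the underlying condition has not worsened, but that complications of such a stay which meet serious criteria must be reported as SAEs.

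Three other provisions bear on the point:
- Section 8.1: "All AEs must be followed to closure".
- Section 8.1.1: "Worsening of pre-treatment events, after initiation of investigational product, must be recorded as new AEs".
- Section 9.9: "Treatment-emergent AEs will be summarized by system organ class and preferred term".

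Sections 8.2.3 and 8.2.5 read the same on this point in the original protocol and in Amendment 1. Amendment 2 keeps 8.2.5 in its table of contents and its summary of changes names no change there, but the supplied text ends in Section 8.1.1.

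**The concern.** The first and third sentences of 8.2.5 agree when an event causes the admission, because admission is normally the moment the serious criterion is met. They disagree when the child is already in hospital. The criterion is then met during the stay, yet the third sentence points back to the admission date.

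The onset date matters in three places. The relatedness guidance in Section 8.1.2 relies on the timing of the event relative to dosing. Section 9.9 summarises treatment-emergent events, and onset date is a likely basis for that classification. The DMC also reviews cumulative safety data about every 3 months, so a wrong date can be in use while the study is running. In a descriptive study of about 5 children, each event will be read almost individually, and a single wrong date is visible.

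**Working it through.** No calculation in the protocol can be reproduced here, because the point concerns a dating rule. The check sets the provisions side by side and applies them to a timeline.

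**Which events are affected**

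| Type of event | General rule (8.2.5, first sentence) | Hospitalization sentence read literally | Agreement |
|---|---|---|---|
| Event that causes the admission | Day of admission | Day of admission | Normally yes |
| Event during a stay that prolongs it | Day within the stay when the criterion is met | Earlier day of admission | No |
| Serious complication of a scheduled-surgery stay | Day the complication becomes serious | Day of an admission that was not an SAE | No |
| Two separate prolonging events in one stay | Two different days | The same day for both | No |

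The third row follows from the protocol's own note in 8.2.3, so the conflict does not depend on any assumption about admission rates.

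**Illustration with assumed days.** Admission Day -3, first dose Day 0, new event that prolongs the stay Day 5, discharge Day 20, symptoms end Day 30.

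- Onset by the general rule: Day 5.
- Onset by the hospitalization sentence: Day -3.
- Error: 5 - (-3) = 8 days too early, and before the first dose.
- SAE record ends on Day 20. Symptoms from Day 20 to Day 30 are recorded as an AE under the next paragraph of 8.2.5 and followed to closure under 8.1.

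If the admission falls after Day 0, the onset is still too early but remains post-dose, so treatment-emergent status is unaffected.

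**Can a stay span the first dose?** Exclusion criterion 18 bars major unscheduled admissions that affect parenteral support within 1 month before or during screening. It exempts uncomplicated bacteremia treatment, central line replacement or repair, and issues of similar size. A stay that spans Day 0 is therefore restricted but possible.

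**What one case amounts to.** Planned enrolment is about 5, so one subject is 1/5 = 20 percentage points of any incidence that depends on the misdated onset. The protocol gives no figure from which the number of prolonging events could be derived.

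**The resolution end.** Discharge usually coincides with the event ceasing to be serious, which fits the second sentence of 8.2.5. It conflicts with that sentence only when the event still meets another criterion at discharge, for example persistent disability.

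**The case against.** The strongest reply is that the hospitalization sentence can be read as covering only events that cause an admission. Section 8.2.3 names admission and prolongation separately, and 8.2.5 opens with a general rule under which a prolonging event could fall. That reading is sensible, and it is what the fix would make explicit. But the text does not state the limit, and investigators at about 5 sites may apply it differently.

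A second reply is that timing is not lost, because 8.1.1 requires post-dose worsening to be entered as a new AE and 8.2.5 requires surrounding symptoms to be recorded as AEs. The investigator also judges relatedness with the clinical course known. This stands as mitigation. It does not correct the onset date on the SAE record itself.

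A third reply concerns frequency. Criterion 18 limits stays around Day 0, and surgery scheduled within the study period is among the example exclusions under criterion 24 (Table 3). This also stands: the situation may be rare.

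Three stronger readings are tempting, but the documents do not support them:
- A reader might infer that unresolved illness is simply shown as resolved at discharge. In fact later symptoms become an AE record and all AEs are followed to closure. The residual weakness is that the later-symptom rule is qualified by investigator discretion.
- A reader might infer that misdated SAEs will drop out of the safety tables. The protocol text supplied does not define treatment-emergence, Section 9.3 leaves analysis definitions to the SAP, and the sentence in 9.9 that counts subjects with SAEs carries no treatment-emergent restriction.
- A reader might infer from exclusion criterion 17 that hospital stays will be common. That criterion caps admissions before screening. It is an eligibility ceiling and says nothing about the rate during the study.

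**Conclusion.** The onset defect holds. Followed literally, 8.2.5 gives an SAE that prolongs an existing stay an onset date before the event occurred, contrary to its own first sentence. This is a stated rule that yields a wrong date, so it is not a detail that can be left to the SAP.

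The shift equals the time from admission to the event: 8 days in the assumed example. Movement from post-dose to pre-dose is conditional on a stay that spans Day 0 and on emergence being judged by the SAE onset date. Where both hold, one case is 20 percentage points with 5 subjects.

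At the resolution end, only a narrow point remains: discharge should not close an SAE that is still serious on another criterion.

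The finding assumes that Amendment 2 carries the same wording, which should be confirmed. The correction is worth making because it is cheap and the sample is very small, but it does not threaten the study's conclusions.

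**What to change.** Replace the hospitalization sentence in Section 8.2.5 with text to this effect:

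> For an SAE that causes an admission, the admission date is the onset date. For an SAE that arises during a stay, including one that prolongs it, the onset date is the date on which the event met a serious criterion. Admission and discharge dates are recorded in their own fields. Discharge alone does not end an SAE that still meets another serious criterion.

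Keep the second sentence of 8.2.5 and the rule on recording later symptoms as an AE. The 8.1 closure definition should not be imported as the SAE resolution rule, because it would conflict with that second sentence, which ends an SAE when it is no longer serious.

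The cost is the replacement of one sentence and a matching line in the eCRF completion guidance. An SAE still serious at discharge would show a longer duration than under the present text. Confirm the Amendment 2 wording of 8.2.5 first.
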